3. STUDY DESIGN

This is a three-arm, open label, randomized, Phase II study comparing the upfront combination of dabrafenib (GSK2118436) with trametinib (GSK1120212) versus the combination after eight weeks of monotherapy treatment with dabrafenib or trametinib.

Approximately 54 eligible patients with histological confirmed cutaneous melanoma that is either metastatic or unresectable (stage IIIc or IV) and BRAF V600E/K mutation positive as determined by a local laboratory will be randomized, 1:1:1 to one of the three treatment arms.

- Arm A: dabrafenib 150mg BID continuously during eight weeks followed by the combination of trametinib 2mg once daily with dabrafenib 150mg BID until disease progression, death or unacceptable toxicity.
- Arm B: trametinib 2mg/day continuously during eight weeks followed by the combination of trametinib 2mg once daily with dabrafenib 150mg BID until disease progression, death or unacceptable toxicity.
- Arm C: trametinib 2mg/day plus dabrafenib 150mg BID continuously until disease progression, death or unacceptable toxicity.

Monitoring will be performed throughout the study according to the Time and Events Table in the protocol.

Biomarker analysis will be performed on blood, tumor and skin samples according to the Time and Events Table in the protocol.

Clinical responses will be evaluated using RECIST 1.1 criteria every 8 weeks. The response evaluation may be performed earlier if clinically indicated (for example, if

patient has symptomatic deterioration suggesting rapid disease progression or to confirm clinical response at 4 weeks after achieving response).

Patients who show either radiographic or clinical progression of disease according to the investigator during the monotherapy treatment period in arm A or B will be able to go on to the combination treatment before completion of the 8 weeks monotherapy treatment. Patients will be treated with the combination treatment until disease progression; unacceptable toxicity or withdrawals from study whichever comes first.

The study will be considered completed when all patients ended study treatment either through progression, death or withdrawal from study for any reason.

4. PLANNED ANALYSES

4.1. Interim Analysis

No interim analyses will be performed for this study.

4.2. Final Analyses

The final analysis will be performed after the last patient has the week 16 efficacy assessment.

5. SAMPLE SIZE CONSIDERATIONS

5.1. Sample Size Assumptions

Based on feasibility a sample size of 54 patients will be enrolled in this trial in 1:1:1 ratio to one of the three treatment arms allowing a total of 20% early dropout rate. Assuming as large as 30% standard deviation (s.d.) of percentage reduction of p-ERK score from baseline, 15 subjects per treatment arm will be sufficient to ensure that the 95% confidence interval (CI) will be the mean \pm 16.61%. With 15 patients per treatment arm, the study will have > 97% power to detect 80% reduction of p-ERK score from baseline to Week 2 within a treatment group (with standard deviation (STD) =70%, alpha=0.05, two sided paired t-test).

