# 9.2. Study Design Considerations

#### 9.2.1. Sample Size Assumptions

Based on feasibility a sample size of 54 patients will be enrolled in this trial in 1:1:1 ratio to one of the three treatment arms allowing a total of 20% early dropout rate. Assuming as large as 30% standard deviation (s.d.) of percentage reduction of pERK score from baseline, 15 patients per treatment arm will be sufficient to ensure that the 95% confidence interval (CI) will be the mean  $\pm 16.61\%$ . With 15 patients per treatment arm, the study will have >97% power to detect 80% reduction of pERK score from baseline to Week 2 within a treatment group (with s.d.=70%, alpha=0.05, two sided paired t-test).

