5.2. Sample Size Sensitivity

The effect of changes in the assumed standard deviation on the precision (i.e., half-width of the 95% CI for percent reduction of p-ERK score from Baseline at Week 2 within a treatment group) is summarized in [Table 1](#).

Table 1 Effects of changes in the assumption of standard deviation

Standard Deviation (%)	Precision (Half-Width of 95% CI of % reduction of pERK score from baseline within a treatment group)
10	5.538
20	11.076
30	16.613
40	22.151
50	27.689

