11.2. Investigator Assessment of H-Score

The primary endpoint analysis will be the evaluation of the percentage change of the mean Phosphorylated Extracellular Signal-regulated Kinase (p-ERK) H-Score from baseline. At the beginning of IP treatment, the p-ERK H-Score will be determined for all participants in the biomarker population.

Change in biomarker status is most prominent within two weeks of start of treatment. Patients from arm A and arm B will be given combination therapy starting from week 9 after completion of 8 weeks of monotherapy. Therefore, changes in biomarker between screening and week 2 as well as between week 8 and week 10 will be summarized and listed. All visits for biomarker samples have a window of ± 7 days.

More specifically, the procedure for calculating the p-ERK score is shown below:

- Intra-tumoral expression levels of ERK, a tumor tissue biomarker, will be measured using immunohistochemistry methods that incorporated both intensity and distribution of staining. A value designated the H-Score will be derived by summing the percentages of cells staining at each intensity multiplied by the weighted intensity of staining (0, 1+, 2+, 3+: 3+ indicates the strongest staining, 2+ indicates medium staining, 1+ indicates weak staining, and 0 indicates no staining). H-Scores range from a minimum score of 0 to a maximum score of 300; the maximum score indicates the strongest expression. We will also collect a summary staining score for the tumor tissue which has potential values of 0 (no staining), 1+ (weak staining), 2+ (medium staining), and 3+ (strong staining).

$$\begin{aligned}
 H - Score &= (3 * \% \text{ Cells with strongest staining}) \\
 &\quad + (2 * \% \text{ Cells with medium staining}) \\
 &\quad + (1 * \% \text{ Cells with weak staining}) \\
 &\quad + (0 * \% \text{ Cells with no staining}) \uparrow
 \end{aligned}$$

All p-ERK H-Score data will be recorded on the eCRF, including data on % positivity for all participants in the biomarker population, which is calculated using the equation below:

$$\begin{aligned}
 \% \text{ Positivity} &= \% \text{ of cells with weak staining} \\
 &\quad + \% \text{ of cells with medium staining} \\
 &\quad + \% \text{ of cells with strong staining} \uparrow
 \end{aligned}$$

Summary statistics, graphics, and statistical modeling will be conducted on the biomarker population for each arm of the study.

11.2.1. Primary p-ERK Biomarker Analyses:

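### The >97% power figure treats percent reduction in p-ERK as normal although it cannot exceed 100%; with that cap and the plan's 70% SD, power is about 85-94% for smooth shapes, and the 95% half-widths are approximate

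*SAP*

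**What the plan says.** SAP 5.1 and Protocol 9.2.1 justify 15 evaluable patients per arm in two ways.

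- **Precision.** The text begins "Assuming as large as 30% standard deviation (s.d.) of percentage reduction of p-ERK score from baseline" and arrives at a 95% interval of the mean ±16.61%. SAP Table 1 and Protocol Table 23 extend this to SDs from 10% to 50%, as the "half-width of the 95% CI for percent reduction of p-ERK score from Baseline at Week 2 within a treatment group".
- **Power.** The SAP says "the study will have > 97% power to detect 80% reduction of p-ERK score from baseline to Week 2 within a treatment group", the conditions being "with standard deviation (STD) =70%, alpha=0.05, two sided paired t-test". The Protocol wording is equivalent: "the study will have >97% power to detect 80% reduction of pERK score from baseline to Week 2 within a treatment group".

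SAP 11.2 defines the score and its limits: "H-Scores range from a minimum score of 0 to a maximum score of 300". SAP 9.2.8 defines percent change as the change divided by the baseline value. Neither sample-size section mentions that a reduction is therefore limited to 100%.

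The sample size itself is set by feasibility. The primary endpoint is descriptive, with no hypothesis test (SAP 2.3, Protocol 9.1).

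**The concern.** A normal distribution centred on an 80% reduction with an SD of 70% is not a possible model for a quantity that stops at 100%. With the mean only 20 points below the limit, an SD of 70 can arise only if a minority of patients have large increases. The distribution is then strongly skewed to the left. With 15 patients, the t-test and t-interval need not have their nominal properties under that skew.

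The power and the half-widths are the only quantitative support that the plan gives for 15 patients per arm on its primary endpoint. If the power is not attainable on the plan's own assumptions, and the intervals cover less often than stated, a reader will take the biomarker estimates to be more secure than they are.

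**Working it through.** **Inputs.** From SAP 5.1: n = 15, mean reduction 80%, SD 70% (power) and 30% (precision), two-sided alpha 0.05, paired t-test. From SAP 5.2: SDs up to 50%. From SAP 11.2 and 9.2.8: score range 0 to 300, with percent change relative to baseline.

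**1. The plan's own figures reproduce under normality.**
- Power: noncentral t with 14 degrees of freedom and noncentrality (80/70) × √15 = 4.43 gives 98.4%, which meets >97%.
- Half-width at SD 30: t(0.975, 14) × 30/√15 = 16.613.

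**2. The normal model breaks the 100% limit.**
- SD 70: P(reduction > 100) = P(Z > 20/70) = 38.8%.
- SD 30: P(Z > 20/30) = 25.2%.

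**3. What mean 80, SD 70 and a cap of 100 imply.** For a variable between m and 100, the variance is at most (100 − 80)(80 − m). Setting 70² = 4900 ≤ 20(80 − m) gives m ≤ −165. The distribution must therefore reach at least a 165% increase, a follow-up/baseline ratio of 2.65. Since the score stops at 300, such a patient needs a baseline of 300/2.65 = 113 or less.

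**4. Power and coverage with the cap imposed.** Let r be the follow-up/baseline ratio, with r ≥ 0, mean 0.20 and the SD shown; the reduction is 100(1 − r). The same t-test and t-interval were applied in 200,000 simulated trials of n = 15. The documents give no distribution, so the shapes are assumptions.

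| Shape of r | Power, SD 70 | Power, SD 30 | Coverage, SD 30 | Coverage, SD 50 |
|---|---|---|---|---|
| Normal (check) | 98.4% | 100% | 95% | 95% |
| Lognormal | 94.2% | 99.2% | 84% | 77% |
| Weibull | 91.5% | 99.8% | 86% | 77% |
| Gamma | 88.5% | 99.9% | 87% | 78% |
| Beta, maximum 3 | 90.7% | 100% | 88% | 79% |
| Beta, maximum 4 | 87.5% | 100% | 88% | 79% |
| Beta, maximum 6 | 85.3% | 100% | 88% | 79% |
| Beta, maximum 10 | 86.7% | 100% | 88% | 79% |
| Two-point | 90.1% | 100% | 95% | 89% |

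At SD 70, every capped shape in the table falls below 97%. Artificial shapes with rare extreme outliers gave 74-93%. The coverage columns assume a true mean of 80%, which the precision statement does not itself specify.

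**The case against.** **The arithmetic is right.** This stands. Both figures reproduce, and a reader who infers a calculation error would be wrong. The problem is the unstated normal assumption.

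**The 70% may be something else.** The 30% SD is explicitly that of the percentage reduction; the 70% is attached only to a paired t-test, and SAP 11.2 speaks of the percentage change of the mean score. If 80% and 70% are paired raw differences scaled to the mean baseline, the per-patient cap does not apply in this form and simulated power exceeds 99%. This reading cannot be excluded, but it is less natural. The effect is given as a reduction from baseline, the endpoint in SAP 2.2.1 is a percentage change, SAP 9.2.8 computes it from each record, and the HScore3 mock-up summarises percentage changes by mean and SD.

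**The shortfall is really about the SD.** For power this stands. A reader might infer that the loss holds whichever SD is chosen; it does not. Under the same capped shapes, power is 99% or more at SD 30. The coverage problem does persist at SD 30 for the smooth shapes, but not for the two-point shape.

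**The simulated shapes are not established either.** Some are unbounded or reach increases that need a low baseline, given the maximum score of 300. The 85-94% range is therefore illustrative and should not be copied into the protocol.

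**Little depends on it.** No test is planned, the sample size rests on feasibility, and SAP 11.2.1 already provides for log2 modelling, medians and nonparametric methods. This limits the consequence but does not make the stated power and half-widths correct.

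**Conclusion.** The point holds on the natural reading that the 70% is the SD of per-patient percent reduction. The >97% is then a normal-theory value for a quantity that cannot be normal. With the cap and the same mean and SD, power is about 85-94% for the smooth shapes tried, and the gap arises from the 70% SD. The requirement in step 3 for large increases from low baselines also makes that SD doubtful in itself.

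The half-widths are correct as normal-theory numbers. With a true mean near 80% and a smooth capped shape, their coverage is about 84-88% at SD 30 and 77-79% at SD 50. At SD 10 it is close to nominal (93-94%).

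Two stronger conclusions are not supported. A reader might infer that the plan's 95% intervals cover only about 70%. That figure belongs to an interval at SD 70, which the plan never gives: the ±16.61% uses SD 30 and the tables stop at 50. A reader might also infer that the trial needs more patients. With a descriptive endpoint and a sample size set by feasibility, nothing here shows that.

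**What to change.** In SAP 5.1 and Protocol 9.2.1, state whether the 70% is the SD of per-patient percent reduction or of the paired difference relative to mean baseline. If it is the former, take one of two routes.

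1. **Keep the percent scale.** Replace >97% with a power simulated under a stated distribution capped at 100%. In SAP 5.2 (Table 1) and Protocol 9.2.2 (Table 23), label the half-widths as normal-theory approximations whose coverage is lower when the mean reduction is close to the cap.
2. **Use the log2 scale planned in SAP 11.2.1.** Give an SD on that scale, account for the offset of 1 used when zero scores occur, and say that the target is then a geometric-mean reduction. This changes the effect: a geometric 80% reduction is log2(0.20) = −2.32, whereas the lognormal shape above, with arithmetic mean 80 and SD 70, has a geometric mean ratio of 0.20/√(1 + 3.5²) = 0.055, or −4.19. The documents give no log-scale SD, so the sponsor must supply one.

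The cost is some wording and a short simulation or recalculation. No extra patients are needed. The downside of the first route is a less favourable stated power.

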5.2. Sample Size Sensitivity

The effect of changes in the assumed standard deviation on the precision (i.e., half-width of the 95% CI for percent reduction of p-ERK score from Baseline at Week 2 within a treatment group) is summarized in [Table 1](#).

Table 1 Effects of changes in the assumption of standard deviation

Standard Deviation (%)	Precision (Half-Width of 95% CI of % reduction of pERK score from baseline within a treatment group)
10	5.538
20	11.076
30	16.613
40	22.151
50	27.689

5.3. Sample Size Re-estimation

Sample size re-estimation is not planned for this study

6. ANALYSIS POPULATIONS

The **Intent-to-Treat Population (ITT)** will consist of all randomized patients whether or not randomized treatment was administered. This population will be based on the treatment to which the patient was randomized and will be the primary population for the analysis of efficacy data. Any patient who receives a treatment randomization number will be considered to have been randomized.

The **Safety Population** will consist of all patients who received at least one dose of randomized treatment and will be based on the actual treatment received. This population will be used for the analysis of clinical safety data.

The **Biomarker Population** will consist of all patients with biopsy performed at screening and at least once during treatment.

7. TREATMENT COMPARISONS

This is a descriptive study and there will be no treatment comparison. Biomarker, efficacy and safety endpoints will be evaluated for each treatment arm.

Depending on the treatment arm, the treatment descriptor will either be listed as **GSK2118436 BID 8W then GSK1120212 QD + GSK2118436 BID** for Arm A, **GSK1120212 QD 8W then GSK1120212 QD + GSK2118436 BID** for Arm B, or **GSK1120212 QD+ GSK2118436 BID** for Arm C.

8. GENERAL CONSIDERATIONS FOR DATA ANALYSES

8.1. Reporting Conventions

Data will be listed and summarized according to GlaxoSmithKline (GSK) current reporting standards where applicable. Integrated Data Standards Library (IDSL) standards will be followed, as appropriate. Reporting and analyses will be performed

using SAS, Version 9.2 or higher. These SAS programs will be imported into HARP and the final output will be produced by running drivers in HARP. Final delivery of all statistical displays will be generated using Clinical Data Interchange Standard Consortium (CDISC) standards. Other software may be used as needed.

Deviations from the analysis in the RAP will be identified in the Clinical Study Report (CSR).

Unless otherwise stated, all listings will be sorted by centre, subject number, and visit. Unless otherwise stated, continuous variables will be summarized with the statistics mean, median, standard deviation, minimum, and maximum. Categorical variables will be summarized with frequency counts and percentages.

Unscheduled visits will be included in the listing using actual time and in calculation of maximum or minimum value over time. However, unscheduled visits will not be included in summaries by planned time.

For summary by planned time, not all plan times are needed to be included in the summary table.

8.2. Multicentre Studies

Data from all participating centres, if applicable, will be pooled prior to analysis. It is anticipated that patient accrual will be spread thinly across centres and summaries of data by centre would be unlikely to be informative and will not, therefore, be provided. However, a summary of subject recruitment by centre will be produced.

8.3. Examination of Subgroups

Exploratory subgroup analyses may be performed, if appropriate. Variables that form the basis of subgroup analyses of some biomarker, safety, and efficacy data including, but not limit to, baseline ECOG performance status, number of prior chemotherapies, age, gender, race and tobacco use.

8.4. Multiple Comparisons and Multiplicity

Adjustment for multiple comparisons is not needed for this study. As there is a single primary endpoint, percentage Change of Erk phosphorylation score from baseline, the nominal levels of significance for the primary analysis will not be affected by multiple comparisons.

9. DATA HANDLING CONVENTIONS

9.1. Premature Withdrawal and Missing Data

Patients will receive study treatment when on combination therapy until disease progression, death or unacceptable adverse event, including haematologic or other nonhaematologic toxicity, and/or meeting stopping criteria for liver chemistry. All

patients will be followed for survival until death, or withdrawal from the study, whichever comes first. A patient will be allowed to continue on monotherapy (either dabrafenib or trametinib) if only one study drug is permanently discontinued.

Note: Continuation of combination study treatment beyond radiographic or clinical disease progression (as defined by RECIST 1.1) may be possible if the investigator determines that patient has clear evidence of clinical benefit from study treatment, continuing study drugs may be in the best interest for the patient and the patient is willing to continue on study drugs. In this case, consultation between the investigator and the GSK Medical Monitor is mandatory. If continuing the patient on study treatment is agreed then all study procedures, including tumor assessments, must be followed as scheduled. In addition, after each tumor assessment, the investigators must confirm with the GSK Medical Monitor that the patient is still benefiting from study treatment and therefore can continue receiving study treatment.

In addition study treatment may be permanently discontinued for any of the following reasons:

- deviation(s) from the protocol
- request of the patient or proxy
- investigator's discretion
- patient is lost to follow-up
- study is closed or terminated.

A patient will be considered to have completed the study if the patient has disease progression or dies during the study treatment. Patients who withdraw from the study will be included in analyses up to the time of withdrawal, regardless of the duration of treatment.

A patient will be considered to have withdrawn from the study if the patient has stopped study treatment due to toxicity, has withdrawn consent, or if the study is closed/terminated.

As the length of treatment for any patient will depend on the efficacy and toxicity of the treatment, the duration of follow-up will vary among patients. Consequently, there will be no imputation for missing data. Answers such as "Not applicable" and "Not evaluable" are not considered to be missing data and should be displayed as such. Subjects with unknown or missing best response will be assumed to be non-responders and will be included in the denominator when calculating percentages.

Subjects with the designation of treatment relationship for adverse events (AEs) and serious adverse events (SAEs) missing will have the worst case assumed to impute the relationship: if the relationship to study treatment is missing, it will be assumed to be "Yes" for summary of drug-related AE or SAE.

In the event that the study is prematurely discontinued, all available data will be listed and a review will be carried out by the study team to assess which statistical analyses are still considered appropriate.

9.2. Derived and Transformed Data

The following sections provide a general description of the derived and transformed variables used to describe and analyze the data. Separate analysis dataset specifications provide full details on all data derivations and transformations including descriptions of standard integrated data standards library (IDSL) algorithms including standard Oncology algorithms. The analysis dataset specifications will clearly communicate the content and source of the datasets supporting the statistical analyses.

9.2.1. Reference dates

There are three reference dates:

- Because age is an eligibility requirement, the reference date for age is the date of screening.
- The safety reference date is the treatment start date, and will be used to calculate study day for safety measures.
- The efficacy reference date is the date of randomization and will be used to calculate study day for efficacy measures and baseline characteristics (such as time since initial diagnosis), as well as efficacy durations.

9.2.2. Study Day for Safety Measures

If the date of interest occurs on or after the safety reference date then the safety study day will be calculated as $(\text{date of interest} - \text{safety reference date}) + 1$. If the date of interest occurs before the safety reference date then the safety study day will be calculated as $(\text{date of interest} - \text{safety reference date})$. There is no safety study day 0.

9.2.3. Study Day for Efficacy

If the date of interest occurs on or after the efficacy reference date then efficacy study day will be calculated as $(\text{date of interest} - \text{efficacy reference date}) + 1$. If the date of interest occurs prior to the efficacy reference date then efficacy study day will be calculated as $(\text{date of interest} - \text{efficacy reference date})$. There is no efficacy study day 0.

